**HP00043324**  
**NCT01250912**

follow-up period. Receiver operating characteristics (ROC) curves will be used to assess best correlation performed with innervation and voltage map.

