**Voltage Map Dataset**

All voltage maps will be created by an electrophysiologist using a Carto 3D mapping system and a 3.5-mm Navistar cooled-tip catheter. Bipolar electrograms will be filtered at 10–30 to 400–500 Hz. Standard clinical voltage criteria will be used to define scar (<0.5 mV), abnormal (0.5–1.5 mV), and normal (>1.5 mV) myocardium. Each voltage map will be divided into 17 segments according to the AHA LV model to conduct visual analysis as well as quantitative analysis.

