**HP00043324**  
**NCT01250912**

### **123I-MIBG Imaging Dataset**

For the planar images a whole-heart region of interest (ROI) will be drawn manually to include both ventricles. A square mediastinal ROI (7x7 pixels) will be drawn in the upper mediastinum, using the apices of the lungs as anatomic landmarks. The H/M ratio will be calculated as the ratio of the counts per pixel in the two ROIs. H/M data will be used to calculate myocardial washout using two formulas. Uncorrected washout will be calculated as

$$H/M (early) - H/M (late) / H/M (early).$$

Background corrected washout will be calculated as

$$H (early) - M (early) - H (late) - M (late) / H (early) - M (early)$$

Single aggregate values for each washout parameter will be determined as described above.

For the SPECT image sets, segmental myocardial activity will be scored using a 17-segment model. Each segment will be scored using the following scale: 0 normal tracer uptake, 1 mildly reduced uptake, 2 moderately reduced uptake, 3 severely reduced uptake, 4 absent tracer uptake, NA not assessable. Accordingly, the summed score (SS) for each study could range from 0 to 68 (17x4).

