**Research Part of the Protocol**

Four specific aims were plan to achieved for this research. Specific Aim 1: Evaluate if areas of left ventricular (LV) denervation measured by cardiac 123I-metaiodobenzylguanidine (MIBG) SPECT imaging (innervation map) can be integrated into the CartoXP electrophysiology mapping system. Specific Aim 2: Evaluate, in a group of 20 patients, if areas of denervation in the 3D maps reconstructed from MIBG SPECT imaging correlate with the voltage-map defined scar targeted during VT ablations Specific Aim 3: Determine the changes of cardiac innervation before and 6 months after the VT ablation in 20 patients. Specific Aim 4: Investigate the possible predicting factors for VT reoccurrence within six month after the ablation.

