**Data Analysis**

Means and standard deviations will be calculated for each of the four registration strategies, i.e. LM, LM and SF, VA, VA and SF, in order to identify the best registration method.

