**HP00043324**  
**NCT01250912**

Differences in scar size, morphology and severity between 3D MIBG innervation maps and EP voltage maps will be analyzed using Student T-test. Segments where diastolic potentials, fractionated potentials and successful ablation sites are located will be investigated in order to identify the characteristics of the MIBG imaging in those segments, e.g. heterogeneity, etc. Segmental/regional washout rate, normalized MIBG activities as well as SS scores will be compared with segmental/regional voltage values in order to identify the relationship between cardiac denervation areas and abnormal endocardial voltage areas.

Differences in size, morphology and severity, regional/global washout from planar images, normalized regional intensities, regional activity summed scores between pre and post ablation 3D MIBG innervation maps will be analyzed using Paired T-test. Global wash out rate will be correlated with HRV indexes before and after the ablation to investigate the relationship between them. Normalized regional MIBG intensities, regional wash out rate and regional SS score both before and after ablations will be compared between VT exit sites segments and other segments with independent sample T-test in order to identify the innervation characteristics of the exit site segments.

Measurements and results will be reported as mean  $\pm$  standard deviation if a normal distribution can be assumed. P values at a level of  $<0.05$  will be considered as statistically significant. Pearson correlation will be conducted to investigate the relationship between two sets of images. The logistic regression will be conducted to investigate the relationship between 3D innervation morphologies, HRV parameters, patient characteristics, clinical VT characteristics and the VT recurrence within the six month

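### The ROC analysis looks for the best innervation–voltage match among several MIBG measures in the same 20 patients, with no primary measure, voltage boundary or unit named and no validation, so the selected result will tend to be optimistic

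*Combined protocol and SAP*

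**What the plan says.** The Combined protocol and SAP gives the ROC analysis one sentence, at the end of Data Analysis: "Receiver operating characteristics (ROC) curves will be used to assess best correlation performed with innervation and voltage map". It names no marker, reference state, unit of analysis, summary measure or cut-off rule.

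- **Candidate measures.** Earlier in Data Analysis: "Segmental/regional washout rate, normalized MIBG activities as well as SS scores will be compared with segmental/regional voltage values". None is primary. Under 123I-MIBG Imaging Acquisition, SPECT is acquired soon after injection and again at 4 hours, so activity and score each exist twice at baseline. Washout combines early and late images into one value. The segment score is ordinal: "Each segment will be scored using the following scale: 0 normal tracer uptake", rising to 4 for absent uptake (123I-MIBG Imaging Dataset).
- **Reference.** Voltage Map Dataset: "Standard clinical voltage criteria will be used to define scar (<0.5 mV), abnormal (0.5–1.5 mV), and normal (>1.5 mV) myocardium". Both boundaries are fixed in advance, but the ROC sentence does not say which one separates diseased from healthy.
- **Data.** Aim 2, under Research Part of the Protocol: "Evaluate, in a group of 20 patients, if areas of denervation in the 3D maps reconstructed from MIBG SPECT imaging" correlate with voltage-defined scar. On segments, Voltage Map Dataset says: "Each voltage map will be divided into 17 segments according to the AHA LV model".
- **A further choice from the data.** Data Analysis also seeks the best of several registration methods: "Means and standard deviations will be calculated for each of the four registration strategies".

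No section describes a hold-out set, cross-validation, bootstrap or second cohort, and none labels the ROC result exploratory.

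**The concern.** Looking for the best correlation implies comparing candidates and keeping the winner. The measure that comes out on top in a small sample does so partly by chance, and its ROC performance in that sample then overstates what it would show in new patients. If a threshold is also read off the same curve, a second layer of optimism is added.

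The stated objective is improved guidance of ablation, so readers will take the ROC result as evidence of how well MIBG imaging identifies abnormal-voltage tissue. An inflated figure would make the method look more ready for that use than it is. Because marker, boundary and unit are all open, a reader of the eventual report could not tell how many combinations were tried.

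**Working it through.** The plan gives no AUC, accuracy target, cut-off or sample-size calculation, so there is no figure to reproduce. The check is to count the candidates and then simulate the size of the optimism.

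**1. Number of candidates.** Activity (early, 4-hour) = 2; score (early, 4-hour) = 2; washout = 1. Total 2 + 2 + 1 = 5, from baseline images only and before any choice of voltage boundary or registration method.

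**2. Amount of data.** 20 hearts × 17 segments = at most 340 segments, clustered within 20 patients. Segments scored as not assessable reduce this.

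**3. Model (assumptions, not in the documents).** Normal marker with shift d = √2·Φ⁻¹(AUC) in abnormal segments; true AUC 0.6, 0.7 or 0.8; 20% or 30% of segments abnormal; within-heart correlation 0, 0.2 or 0.4; K candidate measures of equal true AUC, correlated 0.5 with each other. The measure with the highest AUC is kept, and its cut-off maximises J = sensitivity + specificity − 1. There were 500 simulated studies per scenario.

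- AUC optimism = apparent AUC − true AUC.
- J optimism = apparent J − true J at the chosen cut-off c, where true J = Φ(c) − Φ(c − d).

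For scale, the largest attainable true J is 2Φ(d/2) − 1, which is 0.14, 0.29 and 0.45 for AUC 0.6, 0.7 and 0.8.

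**4. Mean optimism by segment, range over all scenarios.**

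| Analysis | AUC | J |
|---|---|---|
| One pre-specified continuous measure | −0.002 to 0.006 | 0.045 to 0.079 |
| Best of 3 | 0.016 to 0.036 | 0.072 to 0.120 |
| Best of 6 | 0.023 to 0.054 | 0.082 to 0.146 |
| One 0–4 score (30% abnormal) | not computed | 0.019 to 0.039 |

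The five candidates counted above lie between the second and third rows. A middle scenario (AUC 0.7, 30% abnormal, correlation 0.2) gives AUC optimism of −0.001, 0.023 and 0.034, and J optimism of 0.051, 0.086 and 0.103, for K = 1, 3 and 6. Halving J gives the average of sensitivity and specificity: 0.072/2 to 0.146/2, or about 4 to 7 percentage points for the best of 3 to 6.

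**5. Second simulation, coded separately.** It used 4 to 8 correlated candidates, about 30% abnormal and within-heart correlation 0.2–0.4, and judged performance in 6,000 new simulated patients. With true AUC 0.64 the selected AUC averaged 0.67–0.69 (excess 0.03–0.05). Apparent J was 0.29–0.32 against 0.19 in new patients (excess 0.10–0.13). With true AUC 0.71, J was 0.39–0.43 against 0.30 (excess 0.09–0.13). These agree with step 4.

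**6. If the unit were the patient.** The plan does not exclude one value per patient. With N = 20 and 30% or 50% abnormal, J optimism is 0.21–0.27 for one measure and 0.28–0.36 for the best of 3. AUC optimism for the best of 3 is 0.061–0.094. The unit therefore needs stating.

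**The case against.** The strongest reply is that the plan does not promise what would be biased. A reader might infer that an innervation cut-off will be derived and its sensitivity and specificity reported from the same segments, and that the published accuracy is bound to be too good. The documents do not support that. The ROC sentence mentions no cut-off, sensitivity, specificity or accuracy, and no section describes a threshold to be carried to later patients. Aim 2 asks only whether denervation and scar correlate. This part of the reply stands, and the J figures are therefore conditional.

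A reader might also infer that the voltage boundary will be tuned to the data. It will not be on the present text: 0.5 and 1.5 mV are standard criteria fixed in advance. The gap is only that the ROC sentence does not say which applies, and neither the choice of boundary nor that of registration method enters the figures in step 4.

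It is also true that one pre-specified measure summarised by AUC needs no validation to be essentially unbiased, that a single 0–4 score has few possible cut-offs and little optimism, and that the bias is an average tendency. With one continuous measure, the 10th percentile of J optimism was below zero in 17 of 18 segment-level scenarios (lowest −0.039). But the plan does not restrict itself to one measure. With the best of 3 or 6, the 10th percentile was above zero in every segment-level scenario (lowest 0.013), and the AUC itself is inflated.

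Finally, a 20-patient, single-group study can reasonably be exploratory. That is an argument for labelling the result so, which the plan does not do.

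**Conclusion.** The concern holds in limited form. Selection of a best match is in the text, several MIBG measures compete with none primary, and the same 20 patients supply both choice and assessment. The reported ROC result for a selected measure will tend to be optimistic: by segment, about 0.02–0.05 in AUC for the best of 3 to 6 measures and, if a data-chosen cut-off is reported, about 0.07–0.15 in sensitivity + specificity − 1.

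These sizes rest on assumed true AUC, prevalence, within-heart correlation and correlation between measures, and on candidates of equal true merit. If one measure were clearly superior, the selection part would be smaller. The underlying defect is that the ROC analysis is not defined. Defining it removes most of the AUC problem at once.

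**What to change.** Replace the ROC sentence in Data Analysis with text along these lines:

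> The main ROC analysis will use one MIBG measure [named, with its acquisition time] against one voltage boundary [0.5 or 1.5 mV, named], by segment. The AUC will be reported with a 95% confidence interval obtained by resampling whole patients. Other measures and the other boundary are exploratory, and the number examined will be reported. If the best of several measures, or a cut-off chosen from the data, is reported, performance will be corrected by leave-one-patient-out cross-validation or a patient-level bootstrap, with the whole selection repeated in each fold or resample. Uncorrected values will be labelled apparent and exploratory.

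All 17 segments of a heart must stay together in every fold or resample. For a selected AUC the bootstrap is the simpler choice, because different folds may select measures on different scales.

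The cost is a few lines of text, a little more analysis work and slightly lower reported figures. No extra patients, scans or procedures are needed.
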